4.2. Statistical Decision Rules

All hypothesis testing will be conducted using two-sided tests with alpha = 0.05 level of significance. Statistical significance of the key-secondary analysis is dependent on first achieving statistically significant results in the primary analysis. No adjustments for Type I error (at 0.05) will be made for multiple comparisons.

If the test result (from the primary efficacy analysis) is significant (p-value ≤ 0.05) and in favor of ziprasidone, then efficacy of flexibly-dosed oral ziprasidone in the treatment of children and adolescents with Bipolar I Disorder (current or most recent episode manic) will be established.

5. ANALYSIS SETS

The following sets are defined for use in the analyses:

- Intent-To-Treat (ITT) Analysis Set.
- Per-Protocol (PP) Analysis Set.
- Safety Analysis Set.

Both the ITT and PP analysis sets will be used in the analyses of all efficacy endpoints, with the ITT being primary. The Safety Analysis Set will be used in the analyses of the safety data. Only the ITT analysis set will be used in the analyses of the CCI outcome measure and special safety assessments (CSSRS data, CDRS, and movement disorder scales).

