9.3. Definition of Study Populations

For this protocol, an intent-to-treat (ITT) analysis set will be defined as the set of all subjects who were randomized, had baseline measurements, took at least 1 dose of study medication (ziprasidone or placebo), and with at least 1 post-baseline visit.

The per-protocol (PP) analysis set will include all patients in the ITT set without major protocol violations considered to impact the interpretation of the primary efficacy endpoint. Protocol deviations will be reviewed to generate the list of subjects with significant deviations to be excluded from the PP analysis set. The PP exclusion criteria will be finalized prior to breaking the blind.

Both the ITT and PP analysis sets will be used in the analyses of all efficacy endpoints, with the ITT being primary. The Safety Analysis Set which includes all subjects who were randomized and took at least 1 dose of study medication (ziprasidone or placebo) will be used in the analyses of the safety data. Only the ITT analysis set will be used in the analyses of the outcome **CCI** [REDACTED] and special safety assessments (CSSRS data, CDRS, and movement disorder scales).

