5.1. ITT Analysis Set

For this protocol, an intent-to-treat (ITT) analysis set will be defined as the set of all patients who were randomized, had baseline measurements, took at least 1 dose of study medication (Ziprasidone or placebo), and with at least 1 post-baseline visit. This definition of ITT may be considered a modified ITT definition; however, it will be referred to as ITT throughout the protocol and the SAP.

5.2. ‘Per Protocol’ Analysis Set

The per-protocol (PP) analysis set will include all patients in the ITT set without major protocol violations considered to impact the interpretation of the primary efficacy endpoint. Protocol deviations will be reviewed to generate the list of subjects with significant deviations to be excluded from the PP analysis set. The PP exclusion criteria will be finalized prior to breaking the blind.

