5.3. Safety Analysis Set

The safety analysis set will include all patients who were randomized and took at least 1 dose of study medication (ziprasidone or placebo).

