5.4. Treatment Misallocations

If a subject was:

- Randomized but not treated, these subjects are by definition excluded from the efficacy and safety analyses as all analysis sets require subjects to receive at least 1 dose of study medication.
- Treated but not randomized, these subjects are by definition excluded from the efficacy and safety analyses since randomized treatment is missing.
- Randomized but took incorrect treatment, then they will be reported under their randomized treatment group for all efficacy analyses but will be reported under the treatment they received for all safety analyses.

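### The suicidality, depression and movement-disorder scales are safety endpoints but are analysed only on the modified ITT set, which leaves a few dosed subjects out of their tables and listings

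*SAP*

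**What the plan says.** SAP Section 5 makes a general rule for safety, "The Safety Analysis Set will be used in the analyses of the safety data", and then an exception to it. "Only the ITT analysis set will be used in the analyses of the" (partly redacted) outcome measure and the "special safety assessments (CSSRS data, CDRS, and movement disorder scales". Protocol 9.3 has the same exception: "Only the ITT analysis set will be used in the analyses of the outcome" measure and the same three groups of scales.

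The two sets differ in who belongs to them:

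- SAP 5.1, ITT: randomized, and "had baseline measurements, took at least 1 dose of study medication (Ziprasidone or placebo), and with at least 1 post-baseline visit". The SAP acknowledges that this is a modified ITT definition.
- SAP 5.3, Safety Analysis Set: "all patients who were randomized and took at least 1 dose of study medication". It requires neither a visit nor a baseline measurement.

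Protocol 2.2.4 lists the C-SSRS, CDRS-R and movement scales among the safety endpoints, and SAP 6.2.2 places them under the heading for safety endpoints. SAP 8.2.5 and Protocol 9.8 say that every randomized subject who received a dose enters the safety analysis. SAP 5.4 has subjects who took the wrong treatment analysed as randomized for efficacy but "reported under the treatment they received for all safety analyses".

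**The concern.** Safety and tolerability form one of the two primary objectives, and these scales carry the systematic data on suicidality, depression and movement disorder. The usual principle is to summarise safety over everyone exposed. Here the scales use a set built for efficacy, so a child who took study drug and was never seen again is counted in the AE tables but not in the suicidality outputs. The two sets of tables then have different denominators.

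The case that matters most is the rarest: a completed suicide after dosing and before any post-baseline visit. The C-SSRS has an item for completed suicide (Protocol 7.2.9.3), and Protocol 7.2.9.2 calls for supplemental information when one occurs. Under the ITT restriction the death would appear among the SAEs and be absent from the suicidality tables.

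The plan also does not say in which arm a misallocated subject is reported when a safety scale is analysed on the ITT set.

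**Working it through.** **Step 1. Who is in the Safety Analysis Set but not in ITT.** Comparing SAP 5.1 with 5.3 leaves two groups of randomized, dosed subjects:

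- Those with no post-baseline visit of any kind. The definition does not name Visit 3. An end-of-treatment visit (Protocol 6.7), an unscheduled visit (6.6) or the Week 5 visit (6.5) keeps a subject in ITT on a plain reading.
- Those without baseline measurements. This group should be close to empty: Protocol 4.1 requires a qualifying YMRS at baseline, and 5.3.2 dispenses drug only after all baseline assessments.

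**Step 2. Which outputs in SAP 8.2.6 change.**

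| Output | Effect of the ITT restriction |
|---|---|
| Change-from-baseline descriptive statistics | None; both values are needed on any set |
| MMRM for the movement scales | None; it needs a baseline and at least one post-baseline score |
| C-CASA frequencies at screening, baseline and later visits | Screening and baseline counts, and any denominator based on the set, leave these subjects out |
| C-CASA and C-SSRS listings | Their collected screening and baseline data are left out |
| CDRS-R listing for a total of 40 or more at any visit | A qualifying screening or baseline score is left out |
| Completed suicide before any post-baseline visit | Outside the suicidality tables; still in the SAE tables |

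**Step 3. Membership and grouping.** SAP 5 settles who is analysed. SAP 5.4 settles the reporting arm, by type of analysis (efficacy or safety) and not by set. The ITT definition does not say that its members are grouped as randomized. Both sections can therefore apply together: ITT members, grouped as treated. What is missing is a statement that this is intended. SAP 6.2 points to as-treated grouping, because the scales are safety endpoints. The efficacy set, and the efficacy MMRM for the movement scales, could lead a programmer to group as randomized.

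**Step 4. Size.** The SAP's planned total reproduces: 111 / (1 − 0.20) = 138.75, which SAP 2.2.1 gives as approximately 138; 138 + 18 = 156; 156 / 2 = 78 per arm. The share of dosed subjects with no post-baseline visit is not in the documents. Assuming 1% to 5%:

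- Overall: 0.01 × 156 = 1.56 and 0.05 × 156 = 7.8, so about 2 to 8 subjects.
- Per arm: 0.01 × 78 = 0.78 and 0.05 × 78 = 3.9, so about 1 to 4 subjects, leaving 77 to 74 in ITT.
- One subject in an arm of 78 is 1 / 78 = 1.3 percentage points.
- Illustration with four subjects having an event in an arm, all retained: 4 / 78 = 5.13% on the Safety Analysis Set, against 4 / 77 = 5.19% to 4 / 74 = 5.41% on ITT.
- If one of the four is in an excluded subject: 3 / 77 = 3.90% to 3 / 74 = 4.05%.

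For the total of 194 that still stands in the protocol and in SAP 2.1, the same assumption gives 1.94 to 9.7, or about 2 to 10 subjects.

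**The case against.** The case for leaving the rule alone is substantial. It is prespecified, identical in both documents and openly labelled as modified ITT. A subject with no post-baseline visit generally has no post-baseline rating, so moving to a wider set adds almost no scale data after treatment starts. Suicidal acts and movement disorders that qualify as adverse events are still tabulated or listed on the Safety Analysis Set. There is no formal testing of the C-SSRS. All of this stands and limits the size of the point. It does not cover the C-CASA table and the listings, which need no change score, or the completed-suicide case.

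Three stronger readings are tempting and are not supported:

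- A reader might infer that SAP 5 contradicts the as-treated rule in SAP 5.4. Step 3 shows that the two can be applied together; the defect is ambiguity.
- A reader might infer that any child who attempts suicide before Visit 3 drops out of the suicidality tables. A child who survives and attends any later visit stays in ITT, and the protocol requires an end-of-treatment visit, with all Week 4 assessments, to be scheduled for early leavers.
- A reader might infer that the excluded subjects are those most likely to have had an early event. The documents give no data on this. Protocol 1.2.2.1 reports four serious suicide-related events among 193 ziprasidone subjects in the adolescent schizophrenia trial (4 / 193 = 2.1%) and one suicide in its extension. It does not say whether any came before a first post-baseline visit. The earlier trial in this indication reported no suicides and no increase in suicidality.

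**Conclusion.** The point holds as a minor one. Both documents tie safety scales to a set that, by its definition, leaves out some dosed subjects. The consequences are confined to the C-CASA frequency table and its denominators, the C-SSRS/C-CASA and CDRS-R listings, a mismatch with the AE denominators, and the placing of an early completed suicide. The reporting arm for misallocated subjects on these scales is left unclear.

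The estimate of about 2 to 8 subjects rests on an assumed 1% to 5% without a post-baseline visit and on the SAP's 156. If the end-of-treatment visit is obtained reliably, the true number could be near zero. Sample size, power, the efficacy analyses and the AE tables are unaffected.

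**What to change.** In SAP 5, and in Protocol 9.3 to match, assign the C-SSRS/C-CASA, CDRS-R and movement-scale tables and listings to the Safety Analysis Set, grouped by treatment received. Add that change-from-baseline summaries and the movement-scale MMRM use the subjects in that set who have the required values. The ITT rule for the redacted outcome measure can stay.

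If the sponsor prefers to keep ITT for these scales, the SAP should at least say which grouping applies, and should state that a completed suicide before any post-baseline visit is shown with the suicidality tables.

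The cost is a sentence or two in each document, made before unblinding, with no new data. Protocol 9.2 lets the SAP modify the protocol's plans. It asks for an amendment only for major modifications or a significant change to the primary endpoint or its analysis, so the SAP edit may be enough until the protocol text is next revised.

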5.1. ITT Analysis Set

For this protocol, an intent-to-treat (ITT) analysis set will be defined as the set of all patients who were randomized, had baseline measurements, took at least 1 dose of study medication (Ziprasidone or placebo), and with at least 1 post-baseline visit. This definition of ITT may be considered a modified ITT definition; however, it will be referred to as ITT throughout the protocol and the SAP.

5.2. ‘Per Protocol’ Analysis Set

The per-protocol (PP) analysis set will include all patients in the ITT set without major protocol violations considered to impact the interpretation of the primary efficacy endpoint. Protocol deviations will be reviewed to generate the list of subjects with significant deviations to be excluded from the PP analysis set. The PP exclusion criteria will be finalized prior to breaking the blind.

5.3. Safety Analysis Set

The safety analysis set will include all patients who were randomized and took at least 1 dose of study medication (ziprasidone or placebo).

5.4. Treatment Misallocations

If a subject was:

- Randomized but not treated, these subjects are by definition excluded from the efficacy and safety analyses as all analysis sets require subjects to receive at least 1 dose of study medication.
- Treated but not randomized, these subjects are by definition excluded from the efficacy and safety analyses since randomized treatment is missing.
- Randomized but took incorrect treatment, then they will be reported under their randomized treatment group for all efficacy analyses but will be reported under the treatment they received for all safety analyses.

5.5. Protocol Deviations

The following describes any protocol deviations that relate to the PP analysis set stated in [Section 5.2](#):

5.5.1. Deviations Assessed Prior to Randomization

A protocol deviator is a subject who was wrongly enrolled into the study, when inclusion or exclusion criteria were not appropriately satisfied. See protocol sections 4.1 and 4.2.

5.5.2. Deviations Assessed Post-Randomization

Protocol deviations include but are not limited to the following:

- Violations on concomitant medications (See protocol section 5.5);
- Lack of compliance (level to be defined case by case);
- Dosing errors (eg, treatment misallocation, overdose/under-dose).

A full list of protocol deviations will be compiled for the study report prior to database closure. All deviations will be reviewed, and a determination made for the handling of each case. This review will be documented in a note to the study file prior to un-blinding the study database.

6. ENDPOINTS AND COVARIATES

For summaries and analyses of change from baseline, baseline is defined as the pre-dose measurements for variables that have assessment at the Baseline Visit (Day 1), and it is defined as the most recent assessment prior to randomization for variables that have no assessment at the Baseline Visit. For the electrocardiogram (ECG) data, baseline will be defined as the mean of the pre-dose triplicates at the Baseline Visit.

For collection schedules for all endpoints, please refer to the protocol.

6.1. Efficacy Endpoint(s)

6.1.1. Primary Efficacy Endpoint:

- Change from baseline to Week 4 in Young Mania Rating Scale (YMRS) total score.

6.1.2. Key Secondary Efficacy Endpoint:

[figure not shown]
- Change from baseline to Week 4 in Clinical Global Impression of Severity (CGI-S) score.

6.1.3. Secondary Endpoints:

- Change from baseline to Weeks 1, 2 and 3 in the YMRS total score;
- Change from baseline to Weeks 1, 2 and 3 in the CGI-S score;

- CGI-I scores at Weeks 1, 2, 3, and 4.

CCI

6.2. Safety Endpoints

6.2.1. Safety Assessments

- Adverse event monitoring;
- Concomitant treatment monitoring;
- Clinical laboratory monitoring;
- Physical Examinations;
- Blood Pressure and Pulse;
- Height, weight, BMI, BMI z-score, and waist circumference;
- 12-lead ECG.

6.2.2. Special Safety Assessments

- Suicidality assessment monitoring via the Columbia-Suicide Severity Rating Scale (C-SSRS);
- Child Depression Rating Scale - Revised (CDRS-R) monitoring;
- Movement disorder scale (SARS, BAS, and AIMS) monitoring.

6.3. Covariates

Baseline values and weight category will be included as a covariate in the statistical models used to analyze endpoints requiring analysis of covariance (ANCOVA) by the protocol. See [Section 8](#) for details.

7. HANDLING OF MISSING VALUES

For all analyses using mixed model repeated measures models no explicit imputation of missing values will be performed. No imputation techniques (for example: LOCF) will be used for analyzing the endpoint of this study.

8. STATISTICAL METHODOLOGY AND STATISTICAL ANALYSES

8.1. Statistical Methods

8.1.1. Mixed Model Repeated Measures Analyses (MMRM)

The endpoints including the primary, key-secondary, and secondary endpoints will be analyzed using a mixed model repeated measures analysis of covariance (MMRM); treatment, visit, visit-by-treatment interaction, and weight category as fixed effects and baseline score (with the exception of CGI-I score) as a covariate. Subject effect will enter the MMRM model as a random effect. The estimation method used will be restricted maximum likelihood. An unstructured covariance matrix will be used in the REPEATED statement. In case SAS PROC MIXED fails to converge, other covariance matrix structures will be considered in the sequence of Toeplitz, First-Order Autoregressive, and Variance Components. The EMPIRICAL option will be specified to compute the estimated variance-covariance matrix of the fixed-effects parameters. Type III sums of squares will be used to test both main effects and interactions.

8.2. Statistical Analyses

8.2.1. Primary Analysis

The primary efficacy endpoint is change from baseline in the YMRS score. The primary time point is Week 4. The primary endpoint will be analyzed using the MMRM model described in [Section 8.1.1](#). The primary comparison will be between ziprasidone and placebo at Week 4, conducted as a two-sided test at 5% level of significance. Based on the specified model, the point estimate and 95% confidence interval (CI) for the difference in means between the two treatments will be constructed using the least squares means and appropriate standard errors.

If the test result is significant (p-value ≤ 0.05) and in favor of ziprasidone, then efficacy of flexibly-dosed oral ziprasidone in the treatment of children and adolescents with Bipolar I Disorder (current or most recent episode manic) will be established.

A sensitivity analysis will be done by adding an interaction term of treatment and weight category to the primary analysis model specified in [Section 8.1.1](#).

Supplemental analyses of the primary variable will be performed to support the robustness of the conclusions drawn from the primary mixed models repeated measures analysis described above. These supplemental analyses will include the following:

- Summaries of reasons for discontinuations by treatment group;
- Pattern-mixture ANCOVA analysis of change from baseline YMRS scores.

For the pattern-mixture analysis, grouping of the subjects on the basis of their dropout or missing-data patterns will be explored. ‘Patterns’ will be defined under the following two cases:

Case 1:

Pattern 1A - all subjects who have completed the study

Pattern 1B - all subjects who have discontinued the study

Case 2:

Pattern 2A - all subjects who have YMRS score for Week 3 or beyond.

Pattern 2B - all subjects who do not have data beyond Week 2.

A mixed effects repeated measures analysis of covariance model will be used to analyze change from baseline in YMRS score under each of the above cases. These models will include terms for treatment, pattern (as defined above), weight category, treatment-by-pattern interaction, visit, treatment by visit interaction, and visit by pattern interaction as fixed effects, baseline as a covariate, and subject as random effect. The estimation method used will be restricted maximum likelihood. The covariance structure among repeated measures will be assumed to be adequately modeled using an unstructured matrix. In case SAS PROC MIXED fails to converge, other covariance matrix structures will be considered in the sequence of Toeplitz, First-Order Autoregressive, and Variance Components. The EMPIRICAL option (in SAS) will be specified to compute the estimated variance-covariance matrix of the fixed-effects parameters. Type III sums of squares will be used to test both main effects and interactions. The primary comparison will be between ziprasidone and placebo at Week 4, averaged over the missing data patterns, and conducted as a two-sided test at 5% level of significance. Based on the specified model, the point estimate and 95% confidence interval (CI) for the difference in means between the two treatments will be constructed using the least squares means and appropriate standard errors.

The percentage of subjects showing a ≥50% reduction in YMRS scores from baseline to Week 4 will be presented descriptively for each group. Additionally, descriptive statistics for change from baseline in YMRS score will be provided by treatment group and visit classification.

